## 11.2 Analysis

Immunogenicity analyses will be summarized by treatment group (placebo, ALX0-171 3.0 mg/kg, ALX-0171 6.0 mg/kg and ALX-0171 9.0 mg/kg) and overall (ALX-0171 TOTAL).

The incidence of TE ADA and pre-Ab status based on ADA assay results will be tabulated, as well as the incidence of TE ADA and pre-Ab status based on NAb assay results.

All Immunogenicity data will be listed

### 11.2.1 Subgroup analyses

Analysis of incidence based on ADA results are planned for the following subgroups:

- Hypersensitivity reaction, based on the SMQs ‘Hypersensitivity’ (Narrow), ‘Anaphylactic reaction’ (Narrow) and ‘Angioedema’ (Narrow), with categories
  - No hypersensitivity reaction
  - At least 1 hypersensitivity reaction

### 11.2.2 Correlation of immunogenicity with PK, efficacy and safety

The drug concentrations with actual sampling times within time windows per study protocol, will be summarized over time for the subjects with extensive PK sampling, by a subset of ADA (Total Pre-Ab Neg, Total Pre-Ab Pos, Total TE ADA Neg and Total TE ADA Pos) and NAb (Total Pre-dose Neg, Total Pre-dose Pos, Total Neg on treatment and Total Pos on treatment) subject categories. Drug concentrations will also be presented graphically in mean  $\pm$  SE plots. Scatterplots displaying drug concentrations and time will be generated by ADA and NAb subject categories pre-specified above, for each treatment group.

The mean change from baseline (to Day 2, 5 hours post dose) in Global Severity Score (GSS) will be summarized by a subset of ADA (Total Pre-Ab Neg, Total Pre-Ab Pos, Total TE ADA Neg and Total TE ADA Pos) and NAb (Total Pre-dose Neg, Total Pre-dose Pos, Total Neg on treatment and Total Pos on treatment) subject categories, for each treatment group. Scatterplot displaying change from baseline in GSS score (to Day 2,5 hours post dose) will be generated by ADA and NAb subject categories pre-specified above, for each treatment group.

The viral load (time to BQL – plaque assay) will be summarized using Kaplan Meier estimates, by a subset of ADA (Total Pre-Ab Neg, Total Pre-Ab Pos, Total TE ADA Neg and Total TE ADA Pos) and NAb (Total Pre-dose Neg, Total Pre-dose Pos, Total Neg on treatment and Total Pos on treatment) subject categories, for each treatment group. Viral load (time to BQL – plaque assay) will also be presented graphically by Kaplan Meier survival curves for each ADA and NAb subject categories pre-specified above, by treatment group.

## 12 INTERIM ANALYSES

No interim analysis is foreseen for this study.

After the sequential part of the study (see Figure 1: Overview of study design) an evaluation of the relationship between the different ALX-0171 dose levels and the corresponding plasma concentration levels was performed by a separate unblinded team at the CRO. This team remained independent from the main study team to ensure blinding of the study and only provided a general recommendation to the sponsor. Please refer to Appendix B: Concentration assessment plan for more detailed information.

## 13 CHANGE FROM ANALYSIS PLANNED IN PROTOCOL

Additional analysis on the primary endpoint was added using a Cox proportional hazards regression model with time to BQL as dependent variable, and treatment group, viral load at baseline and co-infected subject group as independent variables. These changes will not lead to an amendment of the clinical trial protocol

Following endpoints were added:

- Time between first study drug administration and discharge
- Duration of severe disease
- Duration of feeding support
- Subgroup analyses have been added for selected efficacy and safety endpoints

## 14 CONVENTIONS

### 14.1 General data handling rules

#### 14.1.1 Analysis time points

All by-time-point summaries will be based on the visit indicated on the subject's CRF.

Trial window = (time window, delimited by ICF and trial termination)

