- e. For subjects who discontinue the study before Day 28, the Withdrawal visit will be conducted on the day of withdrawal as long as there has been no withdrawal of consent. If the Withdrawal visit assessments are performed within 6 hours after the Day 1, Day 2, Day 3, or in-hospital post-treatment Day assessments have been performed, the assessments already done at the prior time point do not need to be repeated and only the additional assessments to be performed on the Withdrawal Visit will need to be performed. No EOS visit needs to be performed after the Withdrawal Visit. In case subjects are hospitalized beyond the Day 14 FU visit, the additional assessments (in addition to the in-hospital post treatment period assessments) of the Day 14 FU visit need to be done on Day 14.
- f. RSV infection will be confirmed either according to routine site practice (PCR or diagnostic quick test), or using a (Sponsor-provided) commercial kit.
- g. Hospitalization information will include occurrence of ICU transfer, apnea episodes, initiation and type of ventilation and hospital/ICU discharge information. Assessment of Clinical Response will be done with collection of date and time of adequate oral feeding to enable discharge as well as adequate stable oxygen saturation on room air of  $>92\%$  over a period of at least 4 hours.
- h. Study drug will be administered via nebulization using the study-specific device. One dose consists of 2 serial nebulizations.
- i. A mid-turbinal nasal swab should be taken using provided kits and following specific instructions in case the subject is re-hospitalized or consults the Investigator for a respiratory condition after hospital discharge.
- j. A nasal swab should only be collected during the in-hospital post-treatment period on the day of hospital discharge.
- k. Physical examination includes examination of abdomen and skin and ears/nose/throat. Lung auscultation is listed separately as it is to be assessed more frequently.
- l. Continuous monitoring of SpO2 needs to be done until the clinical response criterion for oxygen has been met and/or in case saturation monitoring is to be continued according to the Investigator's judgment.
- m. Type of feeding support, if any, and feasibility of oral feeding.
- n. To assess wheezing, crackles/crepitation and other abnormalities in lung auscultation.

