### 3.2.3. REMOVAL OF SUBJECTS FROM THERAPY OR ASSESSMENT

Every reasonable attempt should be made by the Investigator (or his/her designee) to keep subjects in the study, however, a subject must be withdrawn from the study if:

- Study drug administration cannot be successfully initiated on Day 1 (see section 3.3.7.2).
- The Investigator considers it, for safety reasons, in the best interest of the subject.
- The parent(s)/legal guardian(s) withdraw(s) consent.

A subject may be withdrawn from the study if the subject and/or parent(s)/legal guardian(s) fail to comply with dosing, evaluations, or other requirements of the study.

Investigators (or their designees) must attempt to contact the parent(s) or legal guardian(s) of subjects who fail to attend scheduled visits by telephone or other means, to exclude the possibility of an AE being the cause of withdrawal. Should this be the cause, the AE must be documented, reported, and followed-up as described in section 3.5.

If a subject is prematurely withdrawn from the study, the reason for withdrawal and the date of withdrawal will be recorded in the eCRF. Whenever possible and reasonable, a Withdrawal visit should be conducted at the time of withdrawal (no EOS visit).

A subject must be discontinued from study drug treatment if:

- The randomization code is broken prematurely by the Investigator or Sub-Investigator.
- A severe and/or serious hypersensitivity reaction occurs
- A severe and/or serious acute respiratory distress reaction induced by study drug administration occurs
- The subject needs to start treatment with one of the medications listed as prohibited (see section [3.3.8](#))
- The subject needs to start non-invasive respiratory support, invasive ventilation or HFOT at levels not enabling removal of the cannula for administration of the study drug nebulization and/or levels exceeding 2 L/kg/min. The event will be captured as an SAE and will be monitored until resolution, as described in section [3.5](#).
- If the investigator or the Sponsor / medical monitor deems it is in the subject's best interest

A subject may be discontinued from study drug treatment if an SAE occurs (if considered necessary or appropriate by the Investigator).

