Subjects having received at least one study drug administration and remaining in the hospital after study drug treatment discontinuation will remain in the study according to the in-hospital post-treatment period specified in the [Schedule of Assessments](#) and should also attend the FU and EOS visits.

If a subject is discontinued from the study and/or study drug, the study monitor and the Sponsor will be informed immediately.

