### **3.3.7.2. ADDITIONAL GUIDANCE**

If dosing cannot be initiated successfully (e.g., because the subject is so agitated as to prevent adequate contact of the face mask with the face, and/or is crying or coughing intensely), new attempts should be made within a maximum of 1 hour (60 minutes) of nebulizer filling.

- If on Day 1, study drug initiation (first of 2 serial nebulizations) has not been successful after 60 minutes, the subject will be withdrawn from the study (see section 3.2.3).
- If on Day 2 or Day 3, study drug initiation (first of 2 serial nebulizations) has not been successful after 60 minutes, study drug treatment should be discontinued (i.e., in case dose initiation was not successful on Day 2, then no dosing on Day 3 should be done). The subjects should remain in the study and all per protocol visits should be conducted according to the [Schedule of Assessments](#).

If the first of the 2 serial nebulizations is started successfully but cannot be continued successfully and needs to be interrupted (e.g., because the subject starts crying intensely, or if the face mask loses adequate contact with the subject's face), study drug administration is to be stopped and resumed as soon as possible and the nebulization should be completed within 2 hours (120 minutes) of nebulizer filling for this nebulization.

The second of the 2 serial nebulizations should be initiated as soon as possible after the end of the first nebulization and should be completed within 2 hours (120 minutes) of nebulizer filling for this nebulization. In case the study drug administration was started successfully but could not be completed, appropriate documentation is needed in the medical file and eCRF but subsequent daily study drug administration should continue per protocol.

The maximum time window allowed to complete both serial nebulizations is 4 hours.

The exact times of study drug administration (i.e., initiation and end of each nebulization and number of interruptions, if any) will be recorded in the eCRF. In addition, acceptability of the face mask and the nebulizer after each complete or partial administration, and whether or not correct and complete administration could be achieved will be documented in the eCRF.

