## 4.2 Sample size

With 45 subjects per arm, 85% power is achieved to detect a 50% reduction in median time-to-BQL (0.5 day with ALX-0171 versus 1 day with placebo) for the plaque assay using a two-sided log-rank test at significance level of 0.05. For each comparison of the ALX-0171 treatment groups with placebo, a significance level of 0.05 is assumed. For multiple pairwise comparisons, the family-wise error rate is controlled at 5% through the closed testing principle, where the comparison of the lower dose of ALX-0171 to placebo is only performed if the comparison of the higher dose of ALX-0171 to placebo is significant. The sample size also incorporates a 15% drop-out rate. With this sample size, a power of 80% is achieved to detect a difference of 2 points in the mean change from baseline (to Day 2 post-dose) on the Global Severity Score for each of the ALX-0171 treatment groups to placebo. This is based on a two-sided t-test with a significance level of 0.05 and assuming a common standard deviation of 3.2 in each group.

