## 7.2 Secondary Efficacy Endpoints Evaluation

### 7.2.1 Key Secondary Endpoint: Global Severity Score (GSS)

- As key secondary endpoint, a formal comparison for change from baseline in GSS (see Section 14.3.2 for computation details) to Day 2, 5 hours post dose will be performed using a contrast analysis on a longitudinal mixed model with random factor subject and fixed effects baseline value, treatment group and timepoint including the treatment-by-timepoint interaction term. All data up to and including Day 3 will be used in the longitudinal mixed model. The Kenward-Roger approximation of degrees of freedom will be used. The model will initially be fitted using an unstructured variance-covariance matrix. In case of non-convergence this may be replaced with a autoregressive variance covariance matrix with heterogeneous variance (ARH) to achieve convergence of the model. The individual pair-wise comparisons will be reported. No formal multiplicity correction will be performed. This comparison will be performed for mITT, RSV infected and PP population.
- For GSS and each of the GSS subitems where GSS is not missing, descriptive statistics will be provided for the actual values and the change from baseline for all planned timepoints. In addition to these planned timepoints, a separate timepoint (Day of hospital discharge) will be created using the last value on the date of discharge from the hospital for GSS summary tables.
- The mean GSS  $\pm$  SE will presented graphically over time (excluding the in-hospital post-treatment assessments), as well as the mean change from baseline  $\pm$  SE. Two bar charts will be provided. One bar chart will present the mean GSS and contributing subitems at all timepoints up to Day 3, 2 hours post dose. The second bar chart will present the mean GSS and contributing subitems over the whole study period (excluding the in-hospital post-treatment timepoints), but will for the first 3 days only include the pre-dose assessments.

Descriptive statistics and figures will be performed on both mITT and RSV infected population

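### GSS scores collected after an early stop of study drug have no route to the Day 2, 5 h contrast, and swabs for these infants pause until discharge, Day 14 or withdrawal

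*SAP*

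**What the plan says.** Protocol 3.2.3 lists the mandatory reasons for stopping study drug. One is: "The subject needs to start non-invasive respiratory support, invasive ventilation or HFOT at levels not enabling removal of the cannula". Others include a severe or serious hypersensitivity reaction, a prohibited medication and a broken code. Infants who have had at least one dose and are still in hospital continue as follows: "remaining in the hospital after study drug treatment discontinuation will remain in the study according to the in-hospital post-treatment period". Schedule footnotes c and d and Protocol 3.4.1.3 say the same. That period has morning and evening assessments that still include the GSS components. Swabs are restricted by footnote j: "A nasal swab should only be collected during the in-hospital post-treatment period on the day of hospital discharge".

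The Schedule also ties every post-dose time point to the end of that day's second nebulization.

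SAP 14.1.1 sets the time points by CRF label: "All by-time-point summaries will be based on the visit indicated on the" CRF. SAP 14.2.2 gives the post-treatment days their own morning and evening intervals for the GSS. SAP 7.2.1 takes the key secondary contrast at Day 2, 5 h from a mixed model and adds: "All data up to and including Day 3 will be used in the longitudinal mixed model".

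For a failed start of dosing on Day 2 or Day 3, Protocol 3.3.7.2 reads differently: "The subjects should remain in the study and all per protocol visits should be conducted according to the" Schedule of Assessments.

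**The concern.** An infant who is given dose 1, deteriorates overnight and starts respiratory support gets no second dose, and so has no visit called Day 2, 5 h. The infant is still scored twice daily, but under labels that no SAP rule links to the key time point. The event that removes the infant is one the GSS is built to register: respiratory support or ventilation earns the maximum 3 points on the medical-interventions item. The model then fills the gap from earlier, better scores as though it were unrelated to the infant's course. The supplementary analyses in SAP 7.2.1 change the population (RSV-infected, per-protocol); none changes this assumption.

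For the primary endpoint, the planned medians are 0.5 and 1 day, so much of the expected separation falls where a Day 1 stopper has no scheduled swab.

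**Working it through.** **1. The plan's own figures.** The SAP states: "With 45 subjects per arm, 85% power is achieved to detect a 50% reduction in median time-to-BQL" (0.5 versus 1 day, two-sided 0.05). By Schoenfeld's formula, events = 4(1.960 + 1.036)²/(ln 2)² = 74.7, so 75, or 37.5 per arm; 37.5/0.85 = 44.1, rounded up to 45. This reproduces.

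For the GSS it states "a power of 80% is achieved to detect a difference of 2 points in the mean change from baseline (to Day 2 post-dose"), with SD 3.2. The normal approximation gives 84.3% at 45 per arm and 78.0% at 45 × 0.85 = 38.25. The stated 80% is just met to within 2 points, with little room for further losses at this time point.

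**2. Which stops matter for the GSS.** Only those before the Day 2, 5 h assessment; later stops leave that value intact. Item-level carry-forward does not help, because SAP 14.2.2 sets the GSS to missing when more than two items are missing.

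**3. How often.** The documents give no stop rate for this trial. The earlier infant study had 2 treatment discontinuations in 53 infants (Protocol 1.2.3), for any cause on any day: 2/53 = 3.8%. If both were on active, with about 35 infants there (3 infants are given as 8.6%), 2/35 = 5.7%.

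**4. Shift in the GSS contrast.** Let non-stoppers differ by −2.0 (active minus placebo). Let stoppers be D points worse than others in their arm, with early stop fractions f_P and f_A. The all-infant difference is −2.0 + D(f_A − f_P). The rates and D are assumptions.

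| f_P | f_A | D = 3 | D = 6 |
|---|---|---|---|
| 10% | 10% | −2.00 | −2.00 |
| 10% | 4% | −2.18 | −2.36 |
| 15% | 5% | −2.30 | −2.60 |
| 4% | 10% | −1.82 | −1.64 |
| 5% | 15% | −1.70 | −1.40 |

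The shift is 0.18 to 0.60 points. For scale, the planned standard error of the contrast is 3.2 × √(2/45) = 0.67. The table takes the analysis to return the non-stoppers' difference; baseline and Day 1 scores may let the model recover part of the shift.

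**5. Primary endpoint.** With exponential times at the planned medians, the fraction not yet BQL at the Day 1, 5 h swab (about 0.22 day) is 2^(−0.22) = 86% on placebo and 2^(−0.22/0.5) = 74% on active. Most infants stopped on Day 1 would therefore have their BQL time set by a much later swab.

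This was simulated with 38 per arm, stoppers having no swab between Day 1, 5 h and discharge at about Day 7, other infants discharged at about Day 4, and a Day 14 swab for all. All of these are assumptions.

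- Power is 79% with no stops, 70% with 4% stopping in each arm and 58% with 10%.
- If the 4% stop only after Day 2, 5 h, power falls by about 1 to 3 points instead.
- With no true effect, stops of 10% on placebo and 4% on active raise false positives favouring active from 2.5% to about 5%.

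**The case against.** The strongest reply is that the SAP 14.1.1 sentence governs by-time-point summaries, not the mixed model, and that SAP 7.2.1 uses all data up to and including Day 3, which might take in post-treatment scores on those calendar days. That stands as an ambiguity: one cannot say the scores are excluded from the model. It does not close the gap. With no mapping rule, they would enter under their own labels and would still not be Day 2, 5 h values.

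A reader might infer that the GSS difference is always pulled toward zero. The table shows otherwise: that holds if placebo stops more, the reverse holds for an otherwise favourable difference if active stops more, and equal rates give no bias.

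A reader might also set the error in one arm's mean against the planned 2-point difference. A 10% stop rate with stoppers 7 points worse gives 0.7, or 35%. That compares unlike quantities, since only the difference in rates moves the contrast. The inputs are also generous. The earlier study's 3.8% covers all causes and days, infants expected to need respiratory support are excluded at entry, and an infant already on oxygen gains only 1 point on the intervention item when support starts.

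For the primary endpoint, it would be too strong to say that clearance in every discontinued infant reflects length of stay. An infant BQL at Day 1, 5 h and confirmed at the next measured swab is dated to Day 1, 5 h. Swabs are also taken at Day 14, at withdrawal and at unscheduled respiratory visits, and unscheduled swabs count (SAP 14.1.3).

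**Conclusion.** The concern holds for stops before Day 2, 5 h (GSS) and for infants stopped on Day 1 or Day 2 who are not yet BQL (primary). Followed as written, the plan gives missingness at the key secondary time point that is caused by the outcome, while the relevant scores sit in the database under another label. The direction follows the between-arm difference in early stop rates, and the size is about 0.2 to 0.6 points against 2 under the assumed ranges. If rates are as low as in the earlier infant study and similar across arms, the GSS effect is small. The primary loss is sensitive to timing: noticeable if stops fall on Day 1, slight if they come after Day 2, 5 h. None of these rates is known for this trial, so the case for acting rests on the mechanism and the low cost of repair.

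Failed starts on Day 2 or Day 3 are a separate uncertainty. Protocol 3.3.7.2 keeps all visits per the Schedule, while the Schedule's own footnotes send discontinued infants to the post-treatment period. The documents do not settle which applies.

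**What to change.** **SAP 14.1.1 and 7.2.1.** For infants off study drug but still in hospital, assign post-treatment GSS assessments to the Day 2 and Day 3 time points by actual time since first dose. For example, take the assessment closest to 29 h (24 h plus 5 h), within 24 to 36 h, as Day 2, 5 h, with similar windows for Day 3. State that these values enter the mixed model. A sensitivity analysis allowing the GSS to be missing not at random, and an interval-censored analysis of time-to-BQL, would show how far the results depend on the gaps that remain.

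The cost is a few lines of SAP text and a windowing step on data already collected. The downside is that the mapped values are not exactly 5 h post-dose.

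**Protocol.** Reconcile 3.3.7.2 with Schedule footnotes c, d and j and with 3.2.3 and 3.4.1.3 on which Day 2 and Day 3 assessments and swabs continue after a stop. SAP 4.1 describes Cohort 4 allocation in the past tense, so for infants already treated only the SAP mapping can still be applied; swabs not taken cannot be recovered.

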### 14.1.2 Relative number of days

The relative day (DY) is calculated as follows:

- = Assessment date – reference date + 1 day, when the assessment date is on or after the reference date
- = Assessment date – reference date, when the assessment date is before the reference date
- = Missing, when the assessment date is missing or incomplete.

The reference date in the study is **date of first dose**, which by definition has DY=1. There is no DY=0.

